# List of Abbreviations

AUC	Area under curve
СІ	Chief Investigator
CRF	Case Report Form
GCP	Good Clinical Practice
ISF	Investigator Site File
IBD	Inflammatory bowel disease
IBS	Irritable bowel syndrome
OGTT	Oral glucose tolerance test
SCFA	Short-chain fatty acid
SOP	Standard Operating Procedure
TMF/SMF	Trial/Study Master File
UoA	University of Aberdeen
UoL	University of Liverpool
VOC	Volatile Organic Compound

### **Protocol Summary**

A dietary intervention study is proposed to investigate the effect, in healthy human volunteers, of dietary lecithin (soy lecithin), a commonly used/consumed emulsifier, on markers of gut function particularly bacterial translocation (assessed by measure of venous blood bacterial DNA, circulating lipopolysaccharide [LPS] binding protein and soluble CD14), gut inflammation (assessed by measurement of faecal calprotectin), gut microbiota activity/composition (faecal short-chain fatty acid [SCFA] profile and bacterial diversity [16S ribosomal RNA genes]) and glucose metabolism (measured by oral glucose tolerance test [OGGT], plasma fasted lipids and insulin).

#### Protocol Summary Diagram

V4 18/02/2019

#### **1.0 Introduction**

Food additives are used for a range of functions in food including:

- To maintain the nutrient composition of the food and to keep it safe to eat
- To make food look or taste better
- To extend the shelf and storage life of a food product
- To improve the nutritional composition of a product (e.g. increase the vitamin content e.g. by adding ascorbic acid)
- Aiding in the processing and manufacture (e.g. emulsifiers, to help mix together ingredients)

This study is interested in the emulsifiers that help mix together ingredients like oil and water that would normally separate, commonly found in mayonnaise. All additives are thoroughly assessed for safety before they are permitted for use, and they are only then permitted to be used in a limited range of products and in certain amounts. Most additives are only permitted to be used in certain foods and are subject to specific quantitative limits. Lecithin is given a number of E322 listed in the FSA website

https://www.food.gov.uk/business-guidance/eu-approved-additives-and-e-numbers

### 1.1 Background literature

Recent research, initially performed on cultured cells and tissues in the laboratory [1] and subsequent studies in mice [2], suggest that some permitted food emulsifiers may cause an increase in bacterial translocation across the gut lining, and/or alterations in the microbiota, with consequent low-level inflammation and altered glucose metabolism. These studies have been performed using a synthetic food emulsifier known as Polysorbate 80, as well as carboxymethylcellulose.

Use of synthetic emulsifiers in foods is however considerably exceeded by the use of natural lecithin, typically sourced from egg or soy, but also consumed in the normal diet in milk or meat. The average diet contains about 1 to 5 g of lecithin per day (WHO [3]). Lecithins contain varying amounts of the phospholipids: phosphatidyl choline (egg lecithin 66 – 80 %, soy c33%), phosphatidyl ethanolamine (egg lecithin c12%, soy 20-30%) and phosphatidyl inositol (egg lecithin c5%, soy c20%) [4, 5]. A single egg yolk contains approximately 1.8g lecithin [4]. In experimental situations, much larger intakes have been studied in man (22 to

83 g per day for 2 to 4 months) without untoward effects and it has not therefore been considered necessary to define a safe limit (WHO [3]).

### 1.2 Rationale for the study

This study primarily aims to determine whether short term (two week) high intake of lecithin alters gut function, as indicated by increased presence of bacterial DNA, soluble CD14 or LPS binding protein in the circulation (venous blood sampling), increased gut inflammation (faecal sampling for white blood cell components such as calprotectin), gut microbiota activity (faecal SCFA and bacterial DNA profile including estimation of diversity) and altered glucose metabolism (assessed by oral glucose tolerance test). This is achieved by comparing a low-emulsifier diet with a diet with soy lecithin emulsifier added – all food is provided to subjects as a controlled diet trial.

### The Research Question

Does dietary intake of soy lecithin alter the intestinal lining and the microbes that normally exist in the intestinal lumen, in healthy subjects, consumed over a two-week period (in comparison to a low-emulsifier diet)?

### 2.0 Study objectives and outcomes

### The Primary Objective:

Assessment of bacterial translocation by venous blood bacterial DNA in response to diet containing soya lecithin emulsifier, in comparison to control period of low-emulsifier diet. Measured as responding to pre and post dietary treatment as gene copy number per ml (as per Gutiérrez *et al.*, 2014 [6]), but using more validated universal qPCR primer sets (including total bacteria, phyla- and class-specific primers as described by Bacchetti De Gregoris *et al.*, 2011 [7]). These data will be backed up by measurement in venous blood of circulating soluble CD14 and LPS binding protein as additional markers of bacterial translocation [8] – see secondary endpoints.

### Secondary endpoints:

Changes in comparison to control (expressed as pre-post change per diet period)

- Faecal calprotectin (Store frozen ELISA @[name] Lab, UoL)
- Faecal volatile organics compounds [VOCs] (Store frozen GC-MS @[name] lab, UoL) [9].
- Faecal microbiota and DNA extraction (Process for SCFA and DNA extraction within 2 weeks, then store frozen bacterial 16S rRNA gene sequencing @[name] Lab, Rowett; UoA).
- Plasma highly sensitive C-reactive protein [hsCRP] (Store frozen ELISA @[name] Lab, UoL; T1,2,3,4 overnight fasted).
- Plasma soluble CD14 and LPS binding protein (Store frozen ELISA @[name] Lab, UoL; T1,2,3,4 overnight fasted).
- Plasma fasting blood glucose and up to 3 hours after OGTT (KONE, Rowett; T1,2,3,4 as Time 0, 30, 60, 90, 120 minutes).
- Plasma fasting lipid profile (KONE, Rowett UoA, T1, 2, 3, 4; overnight fasted)
- Plasma fasted insulin profile and up to 2 hours postprandial OGTT (KONE, Rowett UoA; T1,2,3,4 as Time 0, 30, 60, 90, 120 minutes).
  (with calculation of HOMA and Matsuda index as an estimate of insulin sensitivity [10]
- Plasma trimethylamine-N-oxide (TMAO) as a measure of cardiovascular risk [11] (Rowett UoA; T1,2,3,4 as overnight fasted).

## 3.0 Study design

Diet trial with randomised sequence of delivery of two diets.

Each subject will participate in a 43-day study design as follows:

- 7 days food diary (recording at home, usual diet) (Days -1 to -7)
- 14 days intervention diet (order randomised as low-emulsifier or high-emulsifier fed as low-calorie diet at 100% resting metabolic rate [RMR]) (Days 8-21)
- 7 days washout food diary (recording at home, usual diet) (Days 22-28)
- 14 days intervention diet (order randomised as low-emulsifier or high-emulsifier fed as low-calorie diet at 100% RMR) (Days 29-42)

• Last test day on Day 43

### 3.1 Diet & Study Setting

All food is prepared at the Human Nutrition Unit, Rowett Institute and all measurements. Diets are provided as individual diets calculated to provide 100% resting energy requirements. The lecithin supplement will be soya lecithin granules\* (Lamberts®, a food grade product, manufactured under GMP conditions) given as 7.5 g twice daily, incorporated into juices.

\*Containing, per 7.5 g; – phosphatidyl choline 1.7 g, phosphatidyl ethanolamine 1.5 g, phosphatidyl inositol 1.1 g, phosphatidic acid 0.6 g, phosphatidyl serine 0.075 g and fatty acids 3.8 g of which 0.9 g saturated, 0.3 g monounsaturated, 2.5 g polyunsaturated.

Selection of the source /dose of soy lecithin is based on the following: 7.5 g granules bi-daily (15g daily dose).

- (i) 15g/day is substantially greater than the typical dietary intake of up to 5g/day so should be sufficient to test for possible effects in what is a relatively short-term study;
- Based on previous work by Cobb *et al*. [12] gave healthy volunteers 7.5g three times daily for 4 weeks and did not report any negative effects
- (iii) The supplier's (Lamberts®) web site (which implies that lecithin is good for you) states, "Daily intake 7.5 to 15 grams". Lamberts® as supplier has been selected because they manufacture in the UK according to the stringent pharmaceutical standards of Good Manufacturing Practice (GMP). The soy lecithin granules have "a pleasant mild taste" and are mixed into a fruit/dairy smoothie matrix for stability and compliance.

## **3.2** Participant screening

Initially, participants (n=20 to complete, screening will continue until study completion) will attend a screening visit at the Rowett's Human Nutrition Unit (HNU). This will involve

- self-report general health screening questionnaire
- Height and body weight
- Blood pressure
- completing consent paperwork (PIS and consent form)
- contact details to arrange next appointment to attend the Human Nutrition Unit

Volunteers will then complete a Baseline (Day 1) visit involving:

- RMR measurement for preparation of individual diets
- Height and body weight
- Blood pressure
- Waist and Hip circumference
- Body fat% assessed by BodPod

Volunteers will then be given a 7-day weighed intake food diary to be completed during the initial week washout period of the study (no probiotic or prebiotics to be consumed or antibiotics) to establish their regular eating habits and given a faecal pot to provide a baseline stool sample.

## 3.3 Study Visits

Subsequent study visits will consist of 4 test days when volunteers will be asked to fast overnight before presenting at the HNU. In total there will a baseline visit followed by 4 study visits representing pre-post each diet treatment.

For Test days 1,2,3,4 (Protocol Days 8, 22, 29 and 43; one 6ml EDTA tube and one 6ml LiHep tube and one 2.7ml Li-Hep tube, total 14.7ml whole blood)

 Participants are asked to bring a fresh (<16 h) faecal sample for SCFA and DNA extraction; lab staff to report Bristol stool chart (D8, D22, D29 and D43) & collect VOC.

- Cannulation for blood sampling (D8, D22, D29, D43)
  - $\circ$  T0 Lipid profile (2x200µl plasma), whole blood in LiHep tube 1
  - $\circ~$  T0 Glucose (2x200  $\mu$ l plasma), whole blood in LiHep tube 1
  - $\circ$  T0 Insulin (2x200µl plasma), whole blood in EDTA tube 1
  - T0 Trimethylamine-N-oxide (TMAO), (2x200µl plasma), whole blood in LiHep tube 1
  - $\circ~$  T0 plasma hsCRP (2.7ml whole blood, (2x100 $\mu l$  plasma), whole blood in EDTA tube 1
  - $\circ~$  T0 soluble CD14 and LPS binding protein (2x100 $\mu l$  plasma), whole blood in EDTA tube
  - $\circ$   $\,$  T0 bacterial DNA in sterile tube (1ml whole blood), whole blood in Li-Hep tube
- After ingestion of 75g glucose (Days 8, 22, 29 and 43; one 2.7ml EDTA tube and one 2.7ml LiHep tube for each timepoint, total 21.6ml whole blood)
  - T30, T60, T90, T120 Glucose (2 x 200µl plasma for each timepoint), whole blood in EDTA tube 2,3,4,5
  - T30, T60, T90, T120 Insulin (2 x 200µl plasma for each timepoint) whole blood in LiHep tube 2,3,4,5
- GI discomfort questionnaire [13] (Storey et al 2007, D8, D22, D29, D43)

Total blood is 36.3ml each test day (equivalent to 2 tablespoons) or 145.2 ml over the entire protocol (less than one blood donation). Subjects will receive reimbursement of travel expenses and a small gratuity (up to £50).

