#### 8.0 Labs and Samples Analysis

Faecal samples will be used to determine gut microbiota, SCFA, VOCs and calprotectin. Samples will be collected into a pre-lined faecal collection pot when the participant needs to defecate. The participant will be required to seal the container and return it to the institute within 12 hours for effective microbial microbiome and metabolome profiling (e.g. bacterial 16S rRNA gene/SCFAs/VOCs analysis [9, 14, 15]. Calprotectin concentration in faeces is higher than in plasma and significantly increased levels of calprotectin in stool are found in patients with bowel inflammation (e.g. IBD), whereas it is not elevated in patients with nonorganic, rather functional diseases like irritable bowel syndrome (IBS) [16]. Blood samples will be collected by a trained phlebotomist or research nurse into 2 separate vacutainer tubes (EDTA and lithium hep tubes). Blood samples will be immediately spun in the centrifuge and plasma aliquots placed into Eppendorf tubes (insulin and TMAO (UOA) and hsCRP, sCD14, LPS binding protein (UOL)) and KONE cups (for glucose and lipid analysis). Plasma samples will be stored in a -70°C degree freezer until analysis.

All samples will be collected and stored in anonymised forms. All freezers are calibrated and monitored by the research team. All laboratory analysis of faecal and blood samples will be undertaken at the Rowett Institute by trained laboratory technicians in the analytical laboratories.

Samples will be stored until the study has been completed and then for further 5 years to allow for potential additional analysis in future ethically reviewed and approved studies. After this period, all samples will be destroyed.

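### Do the switched OGTT tube types (3.3) and the two stool age limits (3.3 and 8.0) call for a change to the plan?

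*Combined protocol and SAP*

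**What the plan says.** **Tubes.** Section 3.3 lists the tube for each analyte. At T0, glucose is assigned to "plasma), whole blood in LiHep tube 1" and insulin to "plasma), whole blood in EDTA tube 1". After the glucose drink the assignments are reversed: for glucose at T30, T60, T90 and T120 the entry is "plasma for each timepoint), whole blood in EDTA tube 2,3,4,5", and for insulin it is "plasma for each timepoint) whole blood in LiHep tube 2,3,4,5". Both types are drawn at every post-load time, "one 2.7ml EDTA tube and one 2.7ml LiHep tube for each timepoint". Section 8.0 names the two tube types but does not allocate analytes to them. The layout applies to Days 8, 22, 29 and 43 alike.

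**Stool.** Section 3.3: "Participants are asked to bring a fresh (<16 h) faecal sample for SCFA and DNA extraction". Section 8.0 requires the participant to "return it to the institute within 12 hours for effective microbial microbiome and metabolome profiling", with the example "bacterial 16S rRNA gene/SCFAs/VOCs analysis".

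**Endpoints.** Section 2.0 places OGTT glucose and insulin, HOMA, the Matsuda index and all faecal measures among the secondary endpoints, expressed as the pre-post change in each diet period against control. The primary endpoint is bacterial DNA in venous blood, taken at T0 only. Sections 6.0 and 7.0 say that measurements and data collection follow authorised SOPs, which are not part of the documents.

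**The concern.** A glucose or insulin curve is normally measured in one sample type from start to finish. Here both analytes switch plasma type between the fasting and the first post-load sample, without a stated reason. If an assay reads differently in EDTA and in heparin plasma, the step from T0 to T30 mixes a physiological rise with a tube difference. The Matsuda index multiplies fasting values by whole-curve means, so it would absorb that difference, and the shape of each curve would be distorted. Volume does not force the switch, since both tube types are drawn at every time.

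For stool, both sections describe the sample reaching the institute and both cover SCFA and bacterial DNA work. A sample aged 12 to 16 hours is acceptable under 3.3 and late under 8.0, so staff reading the protocol alone have two acceptance rules. At stake would be the insulin-sensitivity indices and the faecal endpoints; the primary endpoint uses neither the OGTT nor stool.

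**Working it through.** **1. Blood volumes (the plan's own figures).** T0: 6 + 6 + 2.7 = 14.7 ml. Post-load: 4 × (2.7 + 2.7) = 21.6 ml. Per test day: 14.7 + 21.6 = 36.3 ml. Four test days: 4 × 36.3 = 145.2 ml. All agree with section 3.3, so the tube list is coherent in number and volume. Only the analyte labels are odd.

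**2. Which quantities can be affected.** HOMA uses T0 only, so it never mixes tube types. The Matsuda index is the one named index that combines T0 with later values.

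**3. Effect on the absolute Matsuda level.** The documents give neither a tube offset nor OGTT values, so these are assumptions: glucose 5.3, 8.5, 8.5, 7.5, 6.8 mmol/L; insulin 10, 60, 70, 55, 45 µU/mL; a proportional offset of 0%, 2% or 5% at T30 to T120.

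Matsuda = 10000 / √(G0 × I0 × Gmean × Imean), with glucose in mg/dL (mmol/L × 18).

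G0 = 5.3 × 18 = 95.4; Gmean = 7.32 × 18 = 131.76; I0 = 10; Imean = 240/5 = 48. Base value: 10000 / √(95.4 × 10 × 131.76 × 48) = 4.071.

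| Offset at T30–T120 | Matsuda at 2% (change) | Matsuda at 5% (change) |
|---|---|---|
| none | 4.071 (0%) | 4.071 (0%) |
| both analytes higher | 3.999 (-1.8%) | 3.895 (-4.3%) |
| both lower | 4.146 (+1.9%) | 4.264 (+4.7%) |
| glucose only higher | 4.037 (-0.8%) | 3.987 (-2.1%) |
| insulin only higher | 4.033 (-0.9%) | 3.977 (-2.3%) |
| glucose higher, insulin lower | 4.076 (+0.1%) | 4.086 (+0.4%) |

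HOMA = 5.3 × 10 / 22.5 = 2.356 in every row.

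**4. Effect on the planned comparison.** Contrast = (soy post − soy pre) − (control post − control pre). Assume that the soy post visit has 0.5 mmol/L more glucose and 10% more insulin at T30 to T120, and that control does not change.

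- No offset: 3.787 − 4.071 = -0.284
- +2% in both: -0.280
- +5% in both: 3.622 − 3.895 = -0.273
- -5% in both: 3.968 − 4.264 = -0.297

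The largest shift is 0.012, which is 0.012 / 0.284, or about 4% of the contrast. If soy has no effect, all four visits carry the same offset and the contrast is exactly 0 in each case.

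**5. Effect of relabelling part-way.** If the tube labels were aligned between one participant's pre and post visits, that period's change would gain the whole offset: at 5% in both, 4.071 − 3.895 = 0.18, or 4.264 − 4.071 = 0.19. That is roughly 15 times the 0.012 from leaving the layout alone (0.18 / 0.012 = 15). Section 3.4 staggers entry from May to December 2019, so an edit made during recruitment could fall inside someone's diet period.

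**6. Stool limits side by side.** Section 8.0 states a requirement (12 hours); section 3.3 states a request (under 16 hours). The 12-hour window lies inside the 16-hour one, so a participant who meets the stricter rule meets both. The gap is 16 − 12 = 4 hours. The share of the 20 × 4 = 80 test-day samples that would fall in it is unknown. Section 2.0 allows two weeks to process stool for SCFA and DNA extraction. That does not settle the arrival limit, but it gives no reason to think that these 4 hours decide the results.

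**The case for a change.** The best case for acting is that both mismatches are plain in the current text, that nothing else in the documents resolves them, and that correction looks almost free: two tube labels and one number, with blood volume, visits and sample size unchanged. The SOPs may settle both points, but they cannot be seen, and the protocol would still contradict itself on stool age. The post-load tube labels may simply be transposed, in which case correcting them is easy. Absolute Matsuda values and curve shapes, if reported, would mix plasma types.

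Most of that stands as a description of the text. Two parts do not carry through. The gain falls on the absolute Matsuda level and the curve shape, whereas the endpoint in section 2.0 is a within-person change compared between diets. And the correction is free only if it precedes the first test day, or at least never falls within a participant's set of visits. Otherwise it breaks the constant layout that protects the comparison.

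**Conclusion.** The inconsistencies are genuine but minor, and the plan need not change. For the tubes, the planned contrast is essentially protected because all four test days share one layout: a true null stays null, and on the assumed curves, soy effect and 5% offset the contrast of -0.284 moves by at most about 0.012. The absolute Matsuda level could move by up to about 4.7% under the same assumptions, or not at all if the two plasma types read alike; HOMA and the fasting values do not move. For stool, the limits are nested and both can be met; no effect on results has been shown. The primary endpoint and the sample size of 20 are untouched.

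This rests on the tube difference being a roughly constant proportion across visits and on the layout being applied as written throughout. Anyone reporting absolute Matsuda values or curve shapes should note which tubes were used. Tidier wording would be a clerical matter and would not improve any planned analysis.

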## 3.4 Timetable

Volunteer schedule for 2019, to complete 20 (10 men and 10 women)

Appointed post-doc to start 4th Feb 2019

2 volunteers – May to June 2019

2 volunteers – June to July 2019

- 2 volunteers July to August 2019
- 4 volunteers August to September 2019
- 4 volunteers September to October 2019
- 4 volunteers October to November 2019
- 2 volunteers November to December 2019

Analysis – Jan to April 2020

Write up – April to June 2020

### **3.5 Study Population**

Twenty completing participants. Should there be any drop-put, we will continue to replace participants until 20 have completed the trial.

Inclusion Criteria: Men and women adults aged 18+ years; BMI ranging from 27-40 kg/m^2; measured at screening visit.

Exclusion Criteria: Potential volunteers will be asked to fill in a health questionnaire to assess their suitability for the study. This information will allow us to exclude and subjects with:

Medication exclusion criteria - antibiotic use within the past 3 months (due to impact on gut microbiota), statins (current), aspirin (current).

Medical exclusion criteria– chronic inflammatory disorders such as rheumatoid arthritis, inflammatory bowel disease; food allergies; self-reported food sensitivity or intolerance; diagnosis of diabetes; pregnant or breastfeeding; unsuitable veins for blood sampling; inability to speak, read and understand English; unable to comply to alcohol free diet for 5 weeks; consumption of nutrition supplements. Soy allergy or intolerance.

### **3.6 Participant Selection and Enrolment**

Recruitment of volunteers will primarily be through press releases and radio adverts followed by word-of-mouth. We will also contact volunteers from previous studies who have consented specifically that they are willing to take part in human intervention studies. We will be putting up small poster adverts in the local Aberdeen area (in community centres, gyms and shops) as well as the University of Aberdeen advertisement screens.

## 3.6.1 Consenting Participants

Participants will receive the Participant Information sheet when they first express an interest in the study and will be asked to return a copy of the general information form to the research team to provide their contact details and basic eligibility information. When they attend the HNU for their first visit they will meet a member of the Research Team who is trained in taking informed consent. This person will ensure the subject understands what the study entails and answer any queries they have. If the subject is happy to proceed then

they and the researcher will sign & date two copies of the study Consent Form. The subject will keep one copy of this form and the researcher the other.

### 3.6.2 Screening for Eligibility

Participants will undertake a screening test day to ensure eligibility. Following the screening all results will be assessed by HNU GP and local PI to ensure eligibility. Participants will be deemed eligible if (i) their health and wellbeing is not at risk by undertaking the study and (ii) they are not on any medication or have any health condition which will impact study outcomes.

The screening will include:

- General health questionnaire
- Height and weight taken to fulfil BMI criteria

Only eligible volunteers based on meeting the inclusion and exclusion criteria will be recruited for this study up to the required number per group. Once this is reached, additional interested volunteers will be thanked for their interest and no data will be collected. Participants who express an interest and attend the health screening will be required to sign the consent form before undertaking any of the screening measures. Participants who are deemed ineligible during the screening will be thanked for their interest and provided with their health screening results. Ineligible participants will be replaced to meet the 20 participants required to complete the study. If participants do not meet the requirements based on any health markers falling outside of normal values -the participant's results will be sent to their GP. Screening results from these participants will be maintained for audit purposes.

